##### 3.2.2 Progression of NCP over 2 years (Primary)

- Binary outcome (Yes, No)
- Based on both quantitative and qualitative reads
  - Among participants without evidence of NCP at entry on the qualitative read, evidence of NCP at 2 years.
  - Among participants with evidence of NCP at entry on qualitative read, >0% increase in NCP volume
  - Participants with discordant outcomes based on qualitative and quantitative reads, progression will be defined by the quantitative read.

##### 3.2.3 NCP on the 2 year CT (supportive)

- Binary outcome (Yes, No)
- Based on qualitative read
- Outcome is defined regardless of availability of an entry scan

3.2.4 NCP volume at 2 years (supportive)

- Continuous outcome
- Based on quantitative read whenever available (including for participants with no evidence of NCP on the corresponding qualitative read).
  - Participants without a quantitative read and no evidence of NCP on the corresponding qualitative read will be assigned a value of zero.
- Outcome is defined regardless of availability of an entry scan

3.2.5 Total plaque volume

- Analogous outcomes to those in Section 3.2.1-3.2.4 but defined based on total plaque volume (rather than NCP)
- Outcomes will be described for the cohort at entry and year 2, with formal comparisons by treatment group.

3.2.6 Change in relative composition of coronary plaque

- Continuous outcome
- Calculated as the ratio of NCP to overall plaque volume

### 3.3 Exploratory Plaque Outcomes

The following are additional CT-related outcomes that will be described for the cohort at entry and year 2, as appropriate. *Note: Not all of these analyses will be included in the primary manuscript; but will be included in the packet of primary analyses for completeness.*

3.3.1 Number of segments with plaque

- Ordinal outcome: (0, 1-2,  $\geq 3$ )
- Based on qualitative read

3.3.2 Number of segments with noncalcified portion

- Ordinal outcome: (0, 1-2,  $\geq 3$ )
- Based on qualitative read

3.3.3 Presence of vulnerable plaque features

- Five binary (Yes, No) outcomes based on the qualitative read
- Presence of any following vulnerable features (main outcome) and the prevalence of each feature descriptively (four outcomes)
  - Positive remodeling
  - Low attenuation plaque
  - Positive remodeling and low attenuation plaque
  - Napkin ring sign

3.3.4 Alternative definition of noncalcified plaque volume, using a threshold of <130 HU

- Continuous outcome:
  - Absolute change: NCP volume at 2 years – NCP volume at entry
  - Percentage change: (NCP volume at 2 years – NCP volume at entry) / NCP volume at entry (Supportive)
- Based on quantitative read whenever available (including for participants with no evidence of NCP based on the corresponding qualitative read).
  - Participants without a quantitative read and no evidence of NCP based on the corresponding qualitative read will be assigned a value of zero for both absolute and percentage change.

3.3.5 Low attenuation plaque volume (<30 HU)

- Continuous outcome
- Based on quantitative read whenever available.

- Participants without a quantitative read and no evidence of low attenuation plaque on the corresponding qualitative read will be assigned a value of zero

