### 9.1.2 Secondary and Supportive Endpoints

- 9.1.2.1 Number of segments with NCP
- 9.1.2.2 Presence and number of each of the following high-risk plaque features
  - Low Hounsfield Unit attenuation by CT assessment
  - Positive remodeling
- 9.1.2.3 Levels at study entry, 4 months, and 2 years, and changes from study entry to 4 months and 2 years in the following biomarkers
  - Markers of HIV-1 disease: CD4 cell count, HIV-1 RNA level (entry to 2 years only)
  - Soluble markers of monocyte activation: sCD163, sCD14, MCP-1
  - Various monocyte populations including %CD14+CD16+ monocytes (entry to 2 years only)
  - Markers of T-cell activation and exhaustion (entry to 2 years only)
  - Markers of inflammation: Lp-PLA2, hsCRP, IL6, troponin
  - Markers of coagulation: D-Dimer and tissue factor (excluding D-Dimer at month 4; D-Dimer will be available at entry and month 24 only)
- 9.1.2.4 Fasting lipid fractions (Total, non-HDL, and HDL cholesterol) and LDL:HDL ratio at study entry, month 4 and 2 years.

9.1.2.5 Fasting insulin, HgbA1c, and HOMA-IR at study entry, month 4, and 2 years (excluding HgbA1c at month 4; HgbA1c will be available at entry and month 24 only).

9.1.2.6 Time to the first major cardiovascular events as defined in [section 9.2.1](#) of REPRIEVE (A5332).

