Failure to start statin : Included per randomized treatment (treatment policy) Change in statin strategy : Included per randomized treatment (treatment policy) Includes discontinuation or change of statin Evidence of critical stenosis at treatment start : Included per randomized strategy (treatment strategy) Interval stent placement or bypass *: Included per randomized strategy (treatment policy strategy) Death prior to Year 2 scan : Treated as missing data (hypothetical policy)	Missing data due to missed visits or unreadable scans will be assumed missing completely at random and ignored i.e., the primary analysis will be a complete case analysis including participants with pair baseline and year 2 scans. Sensitivity analyses will include multiple imputation for missing data.
Population-level summary measure	Analysis approach
Mean change NCP volume over 2 years	Linear regression (normal errors assumption). In the event of extreme violation of normality, outcomes will be log transformed (giving a percentage change interpretation of the treatment effect). Modeling will adjust for CD4 and sex (stratification factors), and for baseline NCP volume.

\* Stented or bypassed coronary artery segments are not considered on the entry and year 2 scan as part of the read protocol for plaque volume.

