### 2.2 Secondary Objectives

- To determine the effects of pitavastatin on the progression of high risk plaque features including low attenuation plaque and positive remodeling.
- To determine the effects of pitavastatin on detailed markers of immune function including, immune activation (%CD14+CD16+ monocytes, sCD163, sCD14, MCP-1 and T-cell markers), inflammation (Lp-PLA2, hsCRP, hs troponin, oxLDL IL-6), coagulation (D-Dimer) and traditional CVD risk indices

including detailed parameters of glucose homeostasis (insulin, glucose and related indices of insulin resistance such as HOMA-IR).

- To determine the relative contributions of baseline and pitavastatin induced changes in HIV-specific immune activation and traditional risk factors, including LDL, on the presence and progression of coronary plaque and high-risk morphological features in HIV.

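### SAP 3.3.5 can fix low-attenuation volume at zero on a scan whose NCP volume is missing, and SAP 3.3.3 drops the protocol's number of each high-risk feature without logging it

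*SAP*

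**What the plan says.** **Low-attenuation volume.** SAP 3.3.5 uses the quantitative read where there is one. Otherwise: "Participants without a quantitative read and no evidence of low attenuation plaque on the corresponding qualitative read will be assigned a value of zero". The parallel rule for NCP volume in SAP 3.2.4 has a stricter condition: "Participants without a quantitative read and no evidence of NCP on the corresponding qualitative read will be assigned a value of zero". SAP 3.2.1 and 3.3.4 use that stricter condition too. SAP 3.2 sets the primary NCP threshold at <350 HU. On scans that cannot be read, SAP 2.1 says: "Missing data due to missed visits or unreadable scans will be assumed missing completely at random and ignored". On disagreement between the two kinds of read, SAP 3.2.2 says: "Participants with discordant outcomes based on qualitative and quantitative reads, progression will be defined by the quantitative read".

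**High-risk features.** Protocol Appendix II 9.1.2.2, under secondary and supportive endpoints, specifies: "Presence and number of each of the following high-risk plaque features", namely low attenuation and positive remodeling. SAP 3.3.3 specifies: "Five binary (Yes, No) outcomes based on the qualitative read" (any feature, plus four descriptive ones). It stands in SAP 3.3, which opens: "The following are additional CT-related outcomes that will be described for the cohort at entry and year 2, as appropriate". The secondary objective in SAP 2.2 is unchanged from the protocol: "To determine the effects of pitavastatin on the progression of high risk plaque features including low attenuation plaque and positive remodeling". SAP 7.2 tests these features by comparing year-2 prevalence between arms with a chi-squared or Fisher test, overall and by presence of NCP at entry. Protocol Appendix II 9.5.2 planned the same comparison.

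**The concern.** Two separate definitions serve the high-risk plaque objective less well than they could.

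The first is an inconsistency between a part and its whole. A scan may show NCP, show no low-attenuation plaque to the reader's eye, and have no quantitative read. Its NCP volume is then missing, but the portion below 30 HU is recorded as exactly 0 mm³. That is a single-value imputation not labelled as one. Because the value counts as observed, the multiple-imputation sensitivity analysis in SAP 4.1 never reaches it.

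The second is an unrecorded reduction of a protocol endpoint. The SAP's Background section says that major changes from the protocol are outlined in the version history. That table records the removal of HgbA1c and the move of CD4 and HIV-1 RNA, but neither the loss of the feature count nor the move of the features to exploratory. A reader comparing the two documents cannot tell whether this was a decision or an oversight. A yes/no outcome also cannot show a change in how many instances of one feature a participant has, which is part of what progression would ordinarily mean.

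**Working it through.** The plan states no power, rate or variance for either outcome, so there is no figure to reproduce. The definitions are compared first; the arithmetic after that is illustration on assumed inputs.

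**1. The zero rule, scan by scan (no quantitative read in any row)**

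| Qualitative read | NCP volume, SAP 3.2.4 | <30 HU volume, SAP 3.3.5 |
|---|---|---|
| No NCP | 0 | 0 |
| NCP seen, low attenuation seen | missing | missing |
| NCP seen, low attenuation not seen | missing | **0** |
| Scan unreadable | missing (SAP 2.1) | missing (SAP 2.1) |

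Only the third row is inconsistent. The SAP itself does not treat not seen as equal to zero: SAP 3.2.1 and 3.2.4 use the measured volume even where the reader saw no NCP, and SAP 3.2.2 lets the quantitative read prevail. SAP 5.3 tabulates qualitative, quantitative and paired reads separately, so it allows for scans with only one kind of read.

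**2. Possible size.** Let f be the share of an arm's scans in the third row, and r their true <30 HU volume relative to the arm mean m. Under the rule the arm mean becomes m(1 − f·r). Neither f nor r is in the documents.

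- f = 2%, r = 25%: 0.02 × 0.25 = 0.5% too low.
- f = 20%, r = 100%: 0.20 × 1.00 = 20% too low.

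For direction, assume true means of 8 mm³ (pitavastatin) and 10 mm³ (placebo), difference −2.0, and r = 100%:

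| f pitavastatin | f placebo | Observed difference |
|---|---|---|
| 5% | 5% | 7.6 − 9.5 = −1.9 |
| 10% | 10% | 7.2 − 9.0 = −1.8 |
| 5% | 10% | 7.6 − 9.0 = −1.4 |
| 10% | 5% | 7.2 − 9.5 = −2.3 |

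Equal shares shrink the difference; unequal shares can shrink or enlarge it.

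**3. What yes/no outcomes can show.** A participant who gains or loses a feature changes category. One with positive remodeling at entry who acquires low attenuation changes on two of the four feature outcomes. One with a single instance of low attenuation at entry and three at year 2 is yes at both times.

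**4. Yes/no against number.** The evaluable number is 800 × 0.85 / 2 = 340 per arm (SAP Appendix I). Assumed: Poisson counts with control mean λ, rate ratio 0.75, two-sided 5%.

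- Yes/no: p₀ = 1 − exp(−λ), p₁ = 1 − exp(−0.75λ), two-proportion z test with pooled null variance.
- Number: power = Φ(|ln 0.75| / se − 1.96), with se² = 1/(340λ) + 1/(340 × 0.75λ).

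For λ = 1.0, se = √(1/340 + 1/255) = 0.0828, so power = Φ(0.2877/0.0828 − 1.96) = Φ(1.51) = 94%.

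| λ | p₀ | p₁ | Power, yes/no | Power, number |
|---|---|---|---|---|
| 0.2 | 18.1% | 13.9% | 32% | 34% |
| 0.5 | 39.3% | 31.3% | 60% | 69% |
| 1.0 | 63.2% | 52.8% | 79% | 94% |
| 2.0 | 86.5% | 77.7% | 85% | 99.8% |

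**The case against.** The case for leaving the text alone has several strands.

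- **These scans have been read.** A reader might infer that scans nobody has read, but which hold plaque, are set to zero. The text does not say that. The rule requires a qualitative read that is negative for low attenuation; a scan with neither read is missing, and a scan where low attenuation was seen is never zeroed. This stands, and limits the problem to one kind of scan.
- **The zero may be a fair guess.** A negative qualitative read is evidence of a small volume. If affected scans truly hold little, omitting them also biases the mean, by f(1 − r)/(1 − f). At f = 10% and r = 25% that is 0.10 × 0.75/0.90 = +8.3%, against −2.5% under the zero rule. This stands as a caution: treating the value as missing makes the assumption visible and consistent with SAP 3.2.4, but does not guarantee a smaller error.
- **No formal result turns on it.** It is tempting to say that SAP 3.3.5 mis-scores the secondary objective, or counts a participant as fully regressed. Neither follows. The test in SAP 7.2 uses the qualitative features of SAP 3.3.3, and SAP 3.3.5 defines no change score.
- **The SAP did not weaken the planned test.** Protocol 9.5.2 already compared year-2 prevalence only, and no test of the number was ever specified. A comparison of year-2 prevalence between randomized arms is also valid. Both points stand. What is lost is the number as a listed endpoint, a record of the change, and the precision that entry status would add.
- **The number may not be recoverable.** The protocol does not define its unit. SAP 3.3.1 and 3.3.2 show segment counts for plaque and its noncalcified portion, but no document confirms such counts for high-risk features. This stands, and the fix allows for it.

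**Conclusion.** The point holds in a limited form, as a minor improvement.

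SAP 3.3.5 applies a looser zero condition than SAP 3.2.1, 3.2.4 and 3.3.4, so a <30 HU volume can be fixed at zero while the NCP volume that contains it is missing. Any bias falls on an exploratory volume. Its size is unknown: the range of 0.5% to 20% of the arm mean rests wholly on assumed values of f and r, and few scans may be affected. A reader might infer a certain pull of the statin effect toward the null; that needs equal shares in the two arms, which the documents do not establish.

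The protocol's number of each high-risk feature is absent from SAP 3.3.3, the features are now exploratory, and neither change is logged. A reader might go further and call change in these features invisible. It is not: gain and loss of a feature show, and the continuous <30 HU volume is kept. What cannot be seen in the yes/no outcomes is a change in the number of instances of one feature. The power cost runs from about 2 points at a mean of 0.2 features to about 15 points at 1.0 or 2.0, under an assumed Poisson model and rate ratio of 0.75. The comparison in SAP 7.2 leaves out the feature's entry status and states no stratification, which fits poorly with an objective of progression.

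**What to change.** 1. **SAP 3.3.5:** assign zero only when there is no quantitative read and the qualitative read shows no NCP. Otherwise treat the volume as missing under SAP 2.1 and 4.1. Keep the present zero rule as a labelled sensitivity analysis, and add the qualitative low-attenuation finding to the imputation model for this outcome. Report the number of affected scans by arm and visit beside the table in SAP 5.3.
2. **SAP 3.3.3:** restore the number of each feature where the reads recorded it, and define its unit. If it was not recorded, or was dropped on purpose, log that and the move to exploratory in the version history, with the reason.
3. **SAP 7.2:** compare year-2 presence and number by arm with the entry value, sex and CD4 in the model, so that the analysis matches objective 2.2. The unadjusted year-2 prevalence can stay as the protocol's comparison.

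The cost is a few lines of SAP text, slightly more analysis, and a few more missing low-attenuation volumes. No new data collection is needed if the feature counts were recorded, which the documents do not confirm.

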### 3.3.6 Stenosis

- Three outcomes based on qualitative read
- Presence of CAD or stenosis >0%
  - Binary (Yes, No)
- CAD severity
  - Ordinal (Minimal, Mild, Moderate, Severe)
    - No stenosis
    - Minimal CAD, stenosis 1-24%
    - Mild CAD, stenosis 25%-49%
    - Moderate CAD, stenosis 50%-69%
    - Severe CAD, stenosis  $\geq 70\%$  or  $\geq 50\%$  left main
- Presence of stenosis  $\geq 50\%$ 
  - Binary (Yes, No)

### 3.3.7 Progression of NCP over 2 years

- Ordinal outcome (Progression, Stable, Regression)
- Based on both quantitative and qualitative reads
  - Progression: *Defined per 3.1.4*
  - Regression:
    - Based on quantitative read:  $>0\%$  decrease in NCP volume over two years.
  - Stable:
    - Based on qualitative read: No evidence of NCP at entry and 2 years.
    - Based on quantitative read: Percentage change in NCP volume between -2% and +2% (including exactly -2% and +2%).
  - For participants with discordant outcomes based on qualitative and quantitative reads, progression will be defined by on the quantitative read.

### 3.3.8 Coronary artery calcium (CAC), Leaman, and Segment Involvement (SIS) scores

- CAC: Continuous and ordinal (0, 1-10, 11-100, 100-300,  $>300$ )
- Leaman: Ordinal (0,  $>0$ -5,  $\geq 5$ )
- SIS: Ordinal (0, 1, 2, 3, 4, 5+)

## 3.4 Markers of Immune Function

Levels at entry, 4 months and 2 years, and changes from study entry to 4 months and 2 years (unless stated otherwise).

- Soluble markers of monocyte activation
  - sCD163, sCD14, MCP-1
- Monocyte populations (entry and 2 years only)
  - %CD14+CD16+ (inflammatory/intermediate) monocytes
    - Classical and non-classical subsets presented descriptively
- Markers of T-cell activation and T-cell exhaustion (entry and Year 2 only)
  - CD38+DR+ on CD4+ and CD8+
- Markers of inflammation:
  - Lp-PLA2, hsCRP, IL6, hs troponin, oxLDL
- Markers of coagulation
  - D-Dimer

Future analyses will interrogate the broader spectrum of immune phenotyping that has been performed on collected PBMCs.

## 3.5 Markers of Glucose Homeostasis

Levels at entry, 4 months and 2 years, and changes from study entry to 4 months and 2 years.

- Fasting insulin, glucose, and HOMA-IR

### 3.6 Descriptive Outcomes

The following REPRIEVE outcome measures will be described by treatment group for the substudy population but since statin effects for these outcomes will be determined based on the full REPRIEVE cohort, formal treatment comparisons will not be performed.

#### 3.6.1 Time to the first major cardiovascular event

- As defined in the REPRIEVE Primary Statistical Analysis Plan

#### 3.6.2 Fasting lipid fractions

- Total, LDL, non-HDL, and HDL cholesterol, and LDL:HDL ratio at study entry, month 4, and 2 years
  - LDL will be reported as calculated LDL if triglycerides  $\leq 400$  mg/d; direct LDL if triglycerides  $> 400$  mg/dL and  $< 500$  mg/dL; LDL will be considered missing if triglycerides  $\geq 500$  mg/dL

## 4 Analysis Sets and Handling of Missing Data

### 4.1 Primary (Intent-to-treat)

The primary ITT sample will include all registered substudy participants who completed their REPRIEVE (A5332) entry visit. Participants registered to the substudy who failed to complete a REPRIEVE (A5332) entry visit will be considered inadvertent enrollments and excluded from all data summaries and analyses.

The primary analyses will assume all missing data are missing completely at random and be ignored. The intercurrent event of participant death during the 2 year follow-up is expected to be rare and will be handled using a hypothetical strategy – that is, outcomes unavailable due to death will be treated as missing data. Baseline and Year 2 outcomes will be described among all participants with data available at the respective time-point; analyses of change will include only participants with paired scans.

Sensitivity analyses will use multiple imputation with randomization stratification factors (sex and CD4 count) plus ASCVD risk score and BMI used to develop the model.

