### 4.2 Per Protocol (Treated)

All analyses will be repeated within a per protocol sample which will be limited to participants who completed 24-months study follow-up on randomized treatment.

Unless the primary sensitivity analyses demonstrate a concern for informative missingness, per protocol analyses will be limited to participants with paired entry and year 2 scans available with no additional sensitivity analyses performed. Cardiovascular risk factors associated with dropping out of the per protocol analysis will be examined.

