## 5.3 CT Scan Availability

Table: CT scan availability

Table denominator is the ITT analysis set; table will be repeated in the per protocol analysis set.

		Total (N=XX)	Treatment Group	
			Pitavastatin (N=XX)	Placebo (N=XX)
Evaluable Entry CT scan	Qualitative read	XX (XX%)	XX (XX%)	XX (XX%)
	Quantitative read	XX (XX%)	XX (XX%)	XX (XX%)
	Paired reads	XX (XX%)	XX (XX%)	XX (XX%)
No Entry CT scan	scan	XX (XX%)	XX (XX%)	XX (XX%)

		Treatment Group		
		Total (N=XX)	Pitavastatin (N=XX)	Placebo (N=XX)
Reason no entry CT scan	Out of window	XX	XX	XX
	Missed visit	XX	XX	XX
	<other reasons>	XX	XX	XX
	Image quality	XX	XX	XX
Evaluatable Year 2 CT scan	Paired reads	XX (XX%)	XX (XX%)	XX (XX%)
	Qualitative read	XX (XX%)	XX (XX%)	XX (XX%)
	Quantitative read	XX (XX%)	XX (XX%)	XX (XX%)
No Year 2 CT scan		XX (XX%)	XX (XX%)	XX (XX%)
Reason no scan	Out of window	XX	XX	XX
	Premature discontinuation	XX	XX	XX
	Missed visit	XX	XX	XX
	<other reasons>	XX	XX	XX
	Image quality	XX	XX	XX
Evaluatable paired scans	Qualitative read	XX (XX%)	XX (XX%)	XX (XX%)
	Quantitative read	XX (XX%)	XX (XX%)	XX (XX%)
	Paired reads	XX (XX%)	XX (XX%)	XX (XX%)

Possible <Other reasons> based on the scan tracking form might include: Refusal, Unable to place IV or other technical issue, Renal insufficiency, Contrast allergy, BMI >40.

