## Appendix I Sample Size Considerations

[Copied Verbatim from the REPRIEVE A5333S Protocol, Version 5.0, Section 9.2.]

The target sample size for the Mechanistic Substudy of REPRIEVE (A5333s) is 800 participants that will be approximately equally distributed between the study arms.

This sample size was determined to have high power to detect clinically relevant differences between the two study groups both with respect to plaque progression (among those with plaque at study entry) and rates of incident plaque (among those plaque-free at entry). Specifically, the total sample size of 800 subjects will provide 90% power to detect a 6% difference between the study groups in the percent change in NCP volume over 2 years among those with plaque at entry and 90% power to detect 13 percentage point difference in the probability of plaque development over 2 years. These effect sizes translate to a combined estimated 14 percentage point difference in the probability of NCP progression over two years and are based on the following assumptions:

50% of study participants will have evidence of NCP at study entry [Lo 2010]

A SD of 20% for the percent change over 2 years among participants with evidence of plaque at entry

An annual rate of incident plaque development of 12% among participants without plaque at entry

15% of participants entering the substudy will not be evaluable for study entry or 2 year NCP volume.

Together, the effects of statins acting in these two groups (those with and without evidence of NCP at study entry) will provide for a 7% lower prevalence of NCP after 2-years of statin treatment. Expectations for NCP prevalence and progression both as a whole and according to whether NCP was present at study entry are illustrated in the table below. These estimates are based on a simulation that further assumed the following:

Average volume NCP 250mm^3 (SD=200) among participants with NCP at entry.

Average volume NCP 40mm^3 (SD=20) at 2 years among participants without NCP at entry without statin treatment.

Average volume NCP 20mm^3 (SD=20) at 2 years among participants without NCP at entry with statin treatment.

NCP distributions were also assumed to follow a gamma distribution with size and shape parameters determine to provide the desire mean and standard deviations.

Table 9.2-1: Cells constituting the primary targeted group comparisons are shown in bold.

		At study entry			At two 2 years						

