		NCP (%)	NCP volume (mm  )		NCP (%)	NCP volume (mm  )		Change in NCP volume (mm  )		Percent change in NCP volume (%) 	
			Mean (SD)	[P5, P95]		Mean (SD)	[P5, P95]	Mean (SD)	[P5, P95]	Mean (SD)	[P5, P95]
Control	Overall 	50%	121 (186)	[0, 509]	59%	140 (210)	[0, 573]	19 (51)	[-21, 103]	17% (33%)	[-10%, 100%]
	No plaque at entry	-	-	21%	9 (19)	[0, 51]	9 (19)	[0, 51]	21% (41%)	[0%, 100%]	
	No plaque at 2 years				-	-	-	-	-	-	
	Plaque at 2 years				40 (20)	[17, 79]	40 (20)	[17, 79]	100% (0%)	[100%, 100%]	
	Plaque at entry	251 (198)	[26, 637]		281 (231)	[28, 730]	30 (68)	[-38, 153]	12% (20%)	[-14%, 49%]	
Statin	Overall 	50%	120 (185)	[0, 507]	52%	127 (198)	[0, 536]	7 (45)	[-42, 76]	7% (24%)	[-17%, 60%]
	No plaque at entry	-	-	8%	2 (8)	[0, 14]	2 (8)	[0, 14]	8% (27%)	[0%, 100%]	
	No plaque at 2 years				-	-	-	-	-	-	
	Plaque at 2 years				23 (19)	[2,60]	23 (19)	[2,60]	100% (0%)	[100%, 100%]	
	Plaque at entry	250 (197)	[26, 633]		262 (216)	[26, 682]	12 (64)	[-66, 123]	5% (20%)	[-21%, 43%]	

 In estimation of overall means, participants without evidence of NCP are assigned a value of 0 for volume and change.

 In estimation of percentage change, participants without evidence of NCP at study entry with NCP at 2 years are assigned a value of 100%.

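### SAP 4.1's multiple-imputation list does not name randomized arm; run as listed, the sensitivity estimate of the statin effect would be pulled toward zero even under missing completely at random

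*SAP*

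**What the plan says.** The primary analysis of NCP change uses participants with paired scans and assumes the rest are missing completely at random (SAP 2.1, estimand table; SAP 4.1). The estimand table adds "Sensitivity analyses will include multiple imputation for missing data" and names no variables. SAP 4.1 is the only place that does: "multiple imputation with randomization stratification factors (sex and CD4 count) plus ASCVD risk score and BMI used to develop the model". For the analysis model, the estimand table states "Modeling will adjust for CD4 and sex (stratification factors), and for baseline NCP volume".

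The sensitivity result has a further use. SAP 4.2 confines the per-protocol analyses to paired scans, with no extra sensitivity analyses, under the condition "Unless the primary sensitivity analyses demonstrate a concern for informative missingness". No threshold is given for such a concern.

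For planning, Appendix I assumes that "15% of participants entering the substudy will not be evaluable for study entry or 2 year NCP volume". The observed fraction is not in the documents.

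**The concern.** An imputation model should contain every term whose effect the analysis will estimate. If arm is left out, missing outcomes in both arms are drawn around the same pooled mean. The completed data then mix real outcomes that differ by arm with imputed ones that do not, and the estimated difference is diluted.

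The dilution does not depend on why data are missing. It appears under the very assumption that the sensitivity analysis is meant to test. A statistician comparing the imputed and complete-case estimates would see a shift toward zero when nothing is wrong, and SAP 4.2 invites reading such a shift as a sign of informative missingness. This is also the only planned analysis that imputes missing year-2 outcomes.

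**Working it through.** **Inputs** (SAP Appendix I and Table 9.2-1)
- 800 participants, about equal arms; 15% non-evaluable, entry and year-2 scans combined.
- Overall mean change in NCP volume: 19 mm³ control, 7 mm³ statin. The table note explains the overall rows: "In estimation of overall means, participants without evidence of NCP are assigned a value of 0 for volume and change".
- With plaque at entry: 30 and 12 mm³.
- Progression: "These effect sizes translate to a combined estimated 14 percentage point difference in the probability of NCP progression over two years".

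**The plan's own figures.** The SAP gives no figure for the imputation analysis. The overall difference is 19 − 7 = 12 mm³. For progression, a normal approximation from the table gives 0.5·Φ(12/20) + 0.5·0.21 = 0.468 for control and 0.5·Φ(5/20) + 0.5·0.08 = 0.339 for statin. The difference is 12.9 points, near the stated 14. The ratio below applies to either value.

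**Change imputed, or year-2 scan missing.** Let m be the fraction imputed in each arm, μ₁ and μ₀ the arm means, and μ̄ the pooled observed mean. Without an arm term:

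estimate = [(1−m)μ₁ + mμ̄] − [(1−m)μ₀ + mμ̄] = (1−m)(μ₁ − μ₀)

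| m | 12 mm³ becomes | 14 points becomes |
|---|---|---|
| 5% (assumed) | 11.4 | 13.3 |
| 10% (assumed) | 10.8 | 12.6 |
| 15% (planned) | 10.2 | 11.9 |
| 20% (assumed) | 9.6 | 11.2 |

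SAP 7.2 fits the regression among participants with plaque at entry. There the planning difference is 30 − 12 = 18 mm³, and 18 × 0.85 = 15.3 mm³.

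**Entry scan missing.** The result now depends on what is imputed.
- Entry and year-2 volumes imputed separately from the four listed variables: only missing year-2 volumes dilute the arm difference, so the ratio is 1 minus the year-2 share. An even split gives 1 − 0.075 = 0.925; entry scans only gives 1.00. A 4000-trial simulation gave 0.94 and 1.00 (standard error 0.008). Shorter runs gave 0.94 to 0.96 and 0.97 to 0.99.
- Each volume used to impute the other: the ratio stays near 0.86 whichever scan is missing. A missing entry volume predicted from the year-2 volume without arm absorbs part of the arm difference.

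**Simulation of the first case.** 2000 trials of 400 per arm were drawn from the planning values, with 20 imputations, Rubin's rules, and a whole-cohort regression of change on arm, entry volume, sex and CD4. All missingness was on the year-2 scan, and the auxiliaries were unrelated to outcome. At 15% missing:

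| Analysis | Estimate (mm³) | SE | Power |
|---|---|---|---|
| Complete case | −11.97 | 3.57 | 92.1% |
| Imputation as listed | −10.17 | 3.62 | 85.2% |
| Listed plus arm | −11.99 | 3.66 | 91.2% |
| Listed plus arm and entry volume | −11.97 | 3.58 | 92.0% |

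The ratio as listed is 10.17/11.97 = 0.850, a shift of about half a standard error. Complete case was significant and the imputed result was not in 6.9% of trials, against 1.5% once arm was added. In a separate simulation, adding entry volume without arm left the ratio at 0.85, and binary progression shrank by the same factor.

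**The case against.** **The list may not be the whole model.** The SAP does not call it exhaustive, and it also omits the imputation method, the number of imputations and whether change or each volume is imputed. A statistician could read it as additions to an analysis model that already contains treatment. The list itself weakens that reading: sex and CD4 are analysis covariates and are named, while entry NCP volume is also one and is not. Still, a reader might infer that the plan excludes arm, and the text does not say so. What stands is that the only written instruction, followed literally, gives a biased result.

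**Imputation is not the only comparative check.** A reader might infer that nothing else re-estimates the statin effect. The estimand table lists year-2 NCP presence and year-2 NCP volume for sensitivity analyses, and SAP 3.2.3 and 3.2.4 define both whether or not an entry scan exists. They re-estimate the effect in a wider set, but they address missing entry scans, not missing year-2 scans. The scan-availability table in SAP 5.3 ("Table denominator is the ITT analysis set; table will be repeated in the per protocol analysis set") and the paired-scan characteristics in SAP 6 are descriptive.

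**The consequence is conservative.** The bias is toward zero, significance usually survives, and a false alarm under SAP 4.2 would prompt more checking, not less. That is correct and limits the weight of the point.

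**The headline size is conditional.** A reader might take 15% shrinkage, or the fall in power from 92% to 85%, as fixed. The ratio depends on what is imputed and which scan is missing. The power figures are for a whole-cohort regression, and no power loss was computed for the SAP 7.2 analysis among those with plaque at entry.

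**Conclusion.** The omission is real and worth correcting, at moderate weight. Run as listed, with the planned 15% non-evaluable, the imputed effect is about 0.85 of the complete-case effect when change is imputed or the year-2 scans are missing. It is about 0.86 if each volume informs the other. It lies between about 0.93 and 1.00 if the volumes are imputed separately and at least half of the missing scans are entry scans.

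This rests on the list being the full imputation model, roughly equal missingness by arm (20% against 10%, in either direction, gave 0.845 to 0.846), and 15% being a planning figure.

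The documents do not support a stronger claim that the substudy's primary finding is at risk: the complete-case estimate does not use the imputation model. What is at risk is the meaning of the sensitivity analysis. Its gap from complete case could come from the imputation model alone and be taken as evidence about missingness.

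**What to change.** Change the SAP 4.1 sentence to: *Multiple imputation will be done separately by randomized arm (or with arm in the imputation model), using sex and CD4 count plus ASCVD risk score and BMI.* In simulation this restored the estimate (ratio 1.00).

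Adding entry NCP volume is optional; at 15% missing it lowers the standard error from 3.66 to 3.58. How to handle missing entry scans can be left to the sponsor's statistician.

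The cost is one phrase. Arm is known for every participant and no new data are needed. If arm was always intended, the edit only records it. If the analysis has been run, the report should say whether arm was included, and the imputation should be repeated if it was not.
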